5.4 Follow-up Procedures

During the postpartum hospital stay, women will continue to receive routine postpartum care at the discretion of their providers.

5.5 Removal of Subjects from Study

Patients can be taken off the study at any time at their own request, or they may be withdrawn at the discretion of the investigator for safety, behavioral or administrative reasons. The reason(s) for discontinuation will be documented and may include:

- Patient voluntarily withdraws from treatment (follow-up permitted);
- Patient withdraws consent (termination of treatment and follow-up);
- Patient is unable to comply with protocol requirements;
- Patient experiences toxicity that makes continuation in the protocol unsafe;
- Treating physician judges continuation on the study would not be in the patient's best interest.
- The study is stopped.

5.6 Protections Against Physical Risk

There is minimal risk to the use of propranolol during labor. This medication is currently employed in clinical use in pregnant women, and other β -blocking medications such as labetalol are commonly used in laboring women in the University of Pennsylvania Health System. A DSMB comprised of individuals who are not investigators on the trial will be utilized to monitor for adverse outcomes. A list of mandatory events that should be reported to the DSMB within 24 hours of occurrence will be supplied to all clinicians and research coordinators managing trial patients. Also all serious adverse events will be recorded and reported to the institutional review board.

5.7 Protection against Loss of Privacy/Breach of Confidentiality

In order to protect a potential subject's privacy, study staff will only approach potential subjects in a private setting. Once consented, we will take multiple steps to protect the study subject from breach of confidentiality. The list linking the subject's name and medical record number will be kept behind the hospital firewall in a password-protected file. This file is only accessible through the hospital server to those individuals given password approval to access the file. Furthermore, the electronic database (REDCap) will be coded with a unique study identifier rather than with any individually identifiable private information. No PHI will be shared with anyone outside the institution.

6 ADVERSE EVENTS

6.1 Adverse Event Monitoring

Adverse event data collection and reporting will be done to ensure the safety of subjects who will be enrolled in the study. Adverse events will be reported in a routine manner at scheduled times during the trial. Additionally, certain adverse events will be reported in an expedited manner to allow for optimal monitoring of patient safety and care.

All patients experiencing an adverse event, regardless of its relationship to study drug/device, will be monitored until:

- the adverse event resolves or the symptoms or signs that constitute the adverse event return to baseline;
- any abnormal laboratory values have returned to baseline;
- there is a satisfactory explanation other than the study drug for the changes observed; or
- death.

6.2 Definitions

6.2.1 Definition of Adverse Event

An adverse event (AE) is any untoward medical occurrence in a patient receiving study treatment and which does not necessarily have a causal relationship with this treatment. An AE can therefore be any unfavorable and unintended sign (including an abnormal laboratory finding), symptom, or disease temporally associated with the use of an experimental intervention, whether or not related to the intervention.

For the purposes of this study, the following will be considered an adverse event:

- Maternal bradycardia < 50 beats per minute within 30 minutes of drug administration
- Maternal hypotension <80/40 mmHg within 30 minutes of drug administration
- Maternal bronchospasm
- Maternal hypoglycemia requiring treatment
- Maternal allergic reaction
- Chorioamnionitis
- Endometritis
- VTE
- Blood transfusion
- Readmission within 7 days
- NICU admission > 48 hours

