4.2 Toxicities

Any patient who receives treatment will be evaluated for toxicity. Each patient will be assessed for the development of toxicity according to vital sign monitoring or symptoms. In the event of developing bradycardia, hypotension, heart block, cardiogenic shock, bronchospasm, anaphylaxis, or signs of an allergic reaction, the second dose will not be administered.

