6.2.3 Serious Adverse Events

A “serious” adverse event is defined in regulatory terminology as any untoward medical occurrence that:

Results in death.

If death results from (progression of) the disease, the disease should be reported as event (SAE) itself.

Is life-threatening (i.e. the patient was at risk of death at the time of the event).

Requires in-patient hospitalization or prolongation of existing hospitalization for \geq 24 hours.

Results in persistent or significant disability or incapacity.

Is an important medical event. Essentially, any event that does not meet the above criteria, but that in the judgment of the investigator jeopardizes the patient, may be considered for reporting as a serious adverse event.

For the purposes of this study, the adverse events that would meet any of these criteria are listed below and will be documented and reported as a SAE. In addition, any unexpected event which the PI believes to have been cause or contributed to by the intervention, regardless of whether it resulted in hospitalization, will also be considered an AE or SAE.

Maternal SAE:

- Maternal death
- ICU admission
- Anaphylaxis
- Hysterectomy

Neonatal SAE:

- Death
- Blood transfusion
- Hypoxic-ischemic encephalopathy (if NICU documents HIE as diagnosis)
- Intraventricular hemorrhage Grade 3 or 4
- Severe respiratory distress (intubation and mechanical ventilation for a minimum of 12 hours)
- Necrotizing enterocolitis or rule out NEC (if NICU documents this)
- Culture proven neonatal sepsis

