7 DRUG/DEVICE INFORMATION

7.1 Propranolol hydrochloride

- Other names for the drug: Inderal
- Classification - type of agent: β -blocker, antiarrhythmic
- Mode of action: Propranolol is a nonselective beta-adrenergic receptor blocking agent that specifically competes with beta-adrenergic receptor stimulating agents for available receptor sites, thereby decreasing chronotropic, inotropic, and vasodilator responses to beta-adrenergic stimulation.
- Protocol dose: 2mg IV; one possible repeat dose \geq 2 hours later
- Route of administration for this study: IV push
- Incompatibilities: there are no medications that are contraindicated for use with propranolol
- Availability: commercially available, on formulary
- Side effects: hypotension, congestive heart failure, bradycardia, heart block, cardiac arrest, bronchospasm, and cutaneous ulcers. (Please refer to the manufacturer's package insert for a complete list of adverse events)
- Nursing implications: Propranolol is excreted in breast milk.

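### The study-specific AE and SAE lists omit cardiac toxicities the protocol itself names, and conflict with its general AE and SAE definitions, so an expected serious cardiac event could be misclassified

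*Combined protocol and SAP*

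**What the plan says.** **Toxicity assessment (4.2).** "Any patient who receives treatment will be evaluated for toxicity", by vital signs or symptoms. The events that withhold the second dose are "bradycardia, hypotension, heart block, cardiogenic shock, bronchospasm, anaphylaxis, or signs of an allergic reaction".

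**Known drug effects (1.2 and 7.1).** Section 7.1 gives the side effects as "hypotension, congestive heart failure, bradycardia, heart block, cardiac arrest, bronchospasm, and cutaneous ulcers". Section 1.2 also names heart failure, heart block and cardiac arrest as reported adverse events. Cardiogenic shock appears there only as a contraindication.

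**AE definition (6.2.1).** A general definition covers any untoward occurrence in a treated patient, whether or not it is related to treatment. A study-specific list of 11 items follows, introduced by "For the purposes of this study, the following will be considered an adverse event".

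**SAE definition (6.2.3).** General criteria come first: death, threat to life, hospitalization or its prolongation, disability, and important medical event. The section then says that "the adverse events that would meet any of these criteria are listed below". The maternal list has four items: death, ICU admission, anaphylaxis and hysterectomy. The one extension is to "any unexpected event which the PI believes to have been cause or contributed to by the intervention", which counts as an AE or SAE.

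**Expectedness and reporting (6.3, 6.4).** Section 6.3 treats events already identified with the agent as expected. Section 6.4.1 sends SAEs to the PI within 24 hours, and 6.4.2 sends other AEs, including expected ones, to annual reporting.

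**The concern.** The protocol gives staff two ways to decide what is an AE or SAE: a broad definition and a short list. For the cardiac effects of a beta blocker the two give different answers. A coordinator working from the definition would record heart block as an AE and, if a general criterion were met, as an SAE. One working from the list would find no entry for it, and a catch-all worded for unexpected events only.

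Classification matters here because little else in the plan would bring such an event to notice. Section 8 names the overall number of SAEs, and the number of a particular type, as possible triggers for a safety review. Section 6.5 sets no stopping rule, 9.4.1 plans no interim analysis, the secondary endpoints in 2.2.2 include no maternal cardiac outcome, and 8.2 specifies no tabulation of adverse events. Section 1.2 already presents the earlier trials as showing that the drug is safe in labor. A zero count obtained under an ambiguous rule should not be added to that claim.

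**Working it through.** **1. The lists side by side**

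| Event | Named in 4.2 | Known effect in 1.2 or 7.1 | On 6.2.1 list | On 6.2.3 maternal list |
|---|---|---|---|---|
| Heart block | yes | yes | no | no |
| Cardiogenic shock | yes | no (contraindication only) | no | no |
| Congestive heart failure | no | yes | no | no |
| Cardiac arrest | no | yes | no | no |
| Bradycardia | yes | yes | below 50 bpm, within 30 min | no |
| Hypotension | yes | yes | below 80/40 mmHg, within 30 min | no |
| Bronchospasm | yes | yes (7.1) | yes | no |
| Anaphylaxis | yes | no | no | yes |
| Allergic reaction | yes | no | yes | no |

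Two of the seven toxicities in 4.2, and two further cardiac effects from 1.2 and 7.1, are on neither list.

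**2. Are the lists closed?** The text supports either reading. The general definitions point to open lists. Three features point to closed ones: 6.2.3 says the qualifying events are those listed; the added clause for unexpected events is needed only if the lists are otherwise complete; and the numerical and time limits on bradycardia and hypotension do little if any untoward occurrence counts anyway.

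**3. A literal run-through.** Take a woman with heart failure that prolongs her stay by 24 hours or more, without ICU admission or death. She meets a general SAE criterion in 6.2.3. Her event is not on the SAE list. Heart failure is a listed effect in 1.2 and 7.1, so on its type it is expected and outside the catch-all. Read literally, it is not an SAE. The same holds for heart block that meets a criterion.

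**4. Scale.** The plan's figure first: 45% versus 30%, two-sided alpha 0.05, power 80%, 1:1 allocation (assumed), no continuity correction.

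n per arm = [1.960 × √(2 × 0.375 × 0.625) + 0.842 × √(0.45 × 0.55 + 0.30 × 0.70)]² / 0.15² = 162.3, rounded up to 163. The total is 326, as stated in 8.1.

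The protocol gives no rate for these events, so the rates below are assumptions. The chance of at least one event among 163 dosed women is 1 − (1 − p)^163:

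| Assumed rate p | Chance of at least one |
|---|---|
| 0.1% | 15% |
| 0.5% | 56% |
| 1% | 81% |

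With zero events in 163, the upper 95% limit is 1 − 0.05^(1/163) = 1.8% one-sided, or 1 − 0.025^(1/163) = 2.2% two-sided. Either limit assumes that all 163 were dosed and that every event was recorded.

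**The case against.** A reader might infer that the known cardiac harms are simply not counted. The documents do not support that, for these reasons.

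- **General definitions.** The definition in 6.2.1 covers all four events, and its list does not say that only those items count. Cardiac arrest plainly meets the life-threatening criterion in 6.2.3. ICU admission and maternal death are listed SAEs, so the worst cases would probably enter that way, though without a cardiac label.
- **Routine reporting.** Section 6.4.2 provides for expected AEs. It acts only once an event has been classed as an AE.
- **Removal record.** Under 4.6, a patient who meets a 4.2 criterion is removed from therapy, and the PI documents the reason in the Case Report Form. Heart block or shock that stops a second dose is therefore recorded somewhere. This need not reach an event after the last dose, and it is a removal reason, not an AE entry.
- **Cardiogenic shock.** It is not listed as a side effect in 1.2 or 7.1, so it may be unexpected and fall within the catch-all if the PI attributes it to the intervention. The package insert, which 6.3 also relies on, is not available to check.
- **Meaning of unexpected.** Section 6.3 confines its definition to expedited reporting, and treats a listed event as unexpected if its severity is not listed. Section 6.2.3 supplies no other definition.
- **Material not seen.** Section 5.6 promises clinicians a list of events to report to the DSMB within 24 hours, and 9.4.1 refers to an attachment. Either might name these events.
- **Rarity and detection.** The exclusions in 3.2 may make the rates low. Section 4.2 relies on vital signs or symptoms and mentions no ECG, so complete capture of heart block could not be claimed even with better lists.

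All of this stands, and it rules out any claim that the events go unrecorded altogether. It does not remove the conflict in 6.2.3, where an event can meet the plan's own seriousness criteria and still fail its rule for reporting an SAE.

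**Conclusion.** The concern holds as a conflict between passages that must be reconciled. Four cardiac events that the protocol names as toxicities or known effects are on neither study list. Read literally, an expected one that meets a seriousness criterion without ICU admission or death would not be classed as an SAE, and so would not enter the SAE counts that section 8 treats as a possible trigger for a safety review. Milder events may be recorded as AEs by some staff and not by others. The catch-all argument is firm for heart block, heart failure and cardiac arrest on the type of event, and weaker for cardiogenic shock.

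The size in events is unknown. The probabilities above rest on assumed rates, 1:1 allocation and 163 dosed women. The zero-event limits would apply only to events that vital signs or symptoms can detect. The change is worth making because it corrects a stated classification rule at almost no cost.

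**What to change.** - **6.2.1 and 6.2.3:** state that the lists are not exhaustive, and that any event meeting a general AE or SAE criterion is recorded as such whether expected or not.
- **6.2.1:** add heart block, cardiogenic shock, congestive heart failure and cardiac arrest as prespecified terms, each classed as serious when it meets a 6.2.3 criterion.
- **6.2.3:** extend the catch-all to expected as well as unexpected events.
- **8.2:** tabulate these events by arm among dosed women, with exact 95% confidence intervals, and note that detection rests on vital signs or symptoms.

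The cost is a few sentences in three sections and a few Case Report Form fields. Section 4.2 already requires every treated woman to be assessed for toxicity, so no procedure is added, and no dosing or treatment rule changes.

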6.2.2 Severity of Adverse Events

The severity of an AE is graded as follows:

Mild (grade 1): the event causes discomfort without disruption of normal daily activities.

Moderate (grade 2): the event causes discomfort that affects normal daily activities.

Severe (grade 3): the event makes the patient unable to perform normal daily activities or significantly affects his/her clinical status.

Life-threatening (grade 4): the patient was at risk of death at the time of the event.

Fatal (grade 5): the event caused death.

6.2.3 Serious Adverse Events

A “serious” adverse event is defined in regulatory terminology as any untoward medical occurrence that:

Results in death.

If death results from (progression of) the disease, the disease should be reported as event (SAE) itself.

Is life-threatening (i.e. the patient was at risk of death at the time of the event).

Requires in-patient hospitalization or prolongation of existing hospitalization for \geq 24 hours.

Results in persistent or significant disability or incapacity.

Is an important medical event. Essentially, any event that does not meet the above criteria, but that in the judgment of the investigator jeopardizes the patient, may be considered for reporting as a serious adverse event.

For the purposes of this study, the adverse events that would meet any of these criteria are listed below and will be documented and reported as a SAE. In addition, any unexpected event which the PI believes to have been cause or contributed to by the intervention, regardless of whether it resulted in hospitalization, will also be considered an AE or SAE.

Maternal SAE:

- Maternal death
- ICU admission
- Anaphylaxis
- Hysterectomy

Neonatal SAE:

- Death
- Blood transfusion
- Hypoxic-ischemic encephalopathy (if NICU documents HIE as diagnosis)
- Intraventricular hemorrhage Grade 3 or 4
- Severe respiratory distress (intubation and mechanical ventilation for a minimum of 12 hours)
- Necrotizing enterocolitis or rule out NEC (if NICU documents this)
- Culture proven neonatal sepsis

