6.4.2 Routine Reporting

All other adverse events- such as those that are expected, or are unlikely or definitely not related to the study participation- are to be reported annually as part of regular data submission.

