8 STUDY DESIGN/STUDY ENDPOINTS

This will be a prospective, double-blind, placebo-controlled, randomized, multi-center study on the effect of propranolol versus placebo on the rate of cesarean delivery for women with prolonged labor. Please refer to section 2.3 for endpoints.

Regarding stopping rules for safety or efficacy, we do not anticipate early termination of the study for either. Issues that would be of concern would be persistent bradycardia or hypotension with therapy and unexpected events. Other findings that could trigger a safety review include the number of SAEs overall, the number of occurrences of a particular type of SAE, severe AEs, or increased frequency of events.

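### The SAE list in section 6.2.3 omits maternal readmission, although in-patient hospitalization is one of that section's own criteria for seriousness

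*Combined protocol and SAP*

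**What the plan says.** Section 6.2.3 gives general criteria for seriousness. One is "Requires in-patient hospitalization or prolongation of existing hospitalization", followed by a threshold of 24 hours or more. The section then turns to this trial and says that "the adverse events that would meet any of these criteria are listed below and will be documented and reported as a SAE". The maternal items are death, ICU admission, anaphylaxis and hysterectomy. The seven neonatal items do not include length of NICU stay.

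Section 6.2.1 lists the occurrences to be treated as adverse events. They include VTE, "Readmission within 7 days" and "NICU admission > 48 hours". None of these three recurs in the SAE list.

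The reporting routes differ by class:

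- Section 6.4.1: the principal investigator is told of any SAE within 24 hours, whatever its attribution, up to 30 days after the last dose.
- Section 5.6: all SAEs go to the IRB.
- Section 6.4.2: all other adverse events "are to be reported annually as part of regular data submission".

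Section 8 names findings that could prompt a safety review. They begin with "the number of SAEs overall, the number of occurrences of a particular type of SAE" and go on to severe adverse events and a rise in event frequency.

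**The concern.** A maternal readmission is an in-patient hospitalization, so the general criterion points to an SAE. The trial-specific sentence says that the qualifying events are the ones listed, and readmission is not among them. Two coordinators could classify the same woman in opposite ways, each following section 6.2.3.

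The omission matters because readmission is a typical way for a serious problem to show itself after discharge, and section 6.4.1 keeps the SAE window open well past discharge. If the list is followed, a qualifying readmission would not reach the principal investigator within 24 hours as an SAE, would not go to the IRB as an SAE, and would not be counted where section 8 relies on SAE numbers.

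**Working it through.** The point rests on a comparison of text.

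**Step 1. Classify each event under both rules.**

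| Event | Section 6.2.1 (AE list) | General criteria, 6.2.3 | SAE list, 6.2.3 |
|---|---|---|---|
| Readmission, to day 7 | Named | Serious (hospitalization) | Absent |
| Readmission, day 8 onward | Not named | Serious (hospitalization) | Absent |
| VTE | Named | Serious if it leads to admission, prolongs a stay by 24 hours or more, or is life-threatening | Absent |
| NICU admission over 48 hours | Named | Serious if it prolongs the neonate's stay by 24 hours or more | Absent |

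The conflict is direct for readmission and conditional for the other two. One ambiguity remains. If the 24-hour threshold applies to hospitalization as well as to prolongation, a readmission shorter than 24 hours is not serious; longer ones still conflict.

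**Step 2. Compare the time windows.** Readmission is bounded at 7 days in section 6.2.1, at 7 days and 4 weeks in the section 2.2.2 maternal composite, and at 30 days from delivery in section 4.5. The SAE window in section 6.4.1 is 30 days from the last dose. A readmission on day 20 is therefore an endpoint event, inside follow-up and normally inside the SAE window, yet it is named on neither list. It would still fall under the general adverse event definition that opens section 6.2.1.

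**Step 3. Check the clauses that reach beyond the list.** Section 6.2.3 has two.

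- It brings in "any unexpected event which the PI believes to have been cause or contributed to by the intervention". This needs the event to be unexpected and attributed to the intervention, and the result may be either an AE or an SAE. Section 6.4.1 asks for SAEs regardless of attribution, so a readmission judged unrelated is not recovered this way.
- The important-medical-event criterion is a matter of investigator judgment. It is written for events that meet none of the other criteria, whereas a readmission already meets one.

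**Step 4. Size.** The only design figure used is the sample size in section 8.1, and it reproduces. With rates of 45% and 30%, two-sided alpha 0.05, 80% power, and 1:1 allocation assumed:

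n per arm = [1.960 × √(2 × 0.375 × 0.625) + 0.842 × √(0.45 × 0.55 + 0.30 × 0.70)]² / 0.15² ≈ 162.3, rounded up to 163, or 326 in total.

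The documents give no readmission rate. For assumed rates p, the expected number of women readmitted is 326 × p, and the chance of at least one is 1 − (1 − p)^326:

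| Assumed rate | Expected number | Chance of at least one |
|---|---|---|
| 0.5% | 1.6 | 80% |
| 1% | 3.3 | 96% |
| 3% | 9.8 | >99.9% |
| 5% | 16.3 | >99.9% |

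The case is likely to arise at any of these rates, but how often is not known.

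**The case against.** The strongest reply is that other safeguards exist and that the consequences are easily overstated. Much of this stands, and it rules out several stronger readings that a reader might infer.

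- *The list is wholly closed.* It is not, because of the two clauses in step 3. Section 6.4.1 also sends serious, unanticipated and possibly related problems to the IRB within 10 business days. These routes depend on judgment or attribution, so they narrow the gap without closing it.
- *Safety review runs only on SAE counts.* Section 8 also names severe adverse events and increased event frequency. Under section 6.2.2 an event that significantly affects clinical status is grade 3, so a VTE or a grave readmission could prompt review without an SAE label.
- *These events would be looked at only in annual reports.* Section 5.6 describes a list of events for DSMB reporting within 24 hours, whose contents are not shown. Section 9.4.1 provides periodic safety monitoring by the principal investigator and periodic reviews by an advisory board. Annual submission cannot be called the only look.
- *Section 6.2.1 declares its events non-serious.* It does not. It defines adverse events, and an event named there may also be serious.
- *VTE and long NICU stays are always serious.* They are serious only when they meet a criterion.
- *Missed readmissions would outnumber the listed maternal SAEs.* The documents give no rate for any of these events, so the comparison has no basis.

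One could also say that the general definition plainly governs and the list only illustrates it. That is a sensible intention, but the sentence introducing the list says otherwise and would need correcting on that reading too.

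**Conclusion.** The contradiction on maternal readmission is real and should be corrected. Read literally, qualifying readmissions, and those VTE and NICU cases that meet a criterion, would miss expedited SAE handling unless a discretionary or attribution-based clause caught them. They would also be missing from SAE counts, which are one of several triggers for safety review.

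The documents do not support saying that such events would escape oversight, since DSMB reporting and the periodic reviews may still pick them up. The number affected is unknown; about 3 to 10 women is an illustration that rests on an assumed 1% to 3% rate in 326. The conclusion assumes that readmission means in-patient admission and, if the 24-hour threshold applies to hospitalization, that the stay is at least that long. Sample size and primary analysis are unaffected.

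**What to change.** 1. In section 6.2.3, reword the sentence that introduces the list to say that SAEs include, but are not limited to, the events named, so that the general criteria govern.
2. Add maternal readmission through the 30-day follow-up to the maternal SAE list, and state whether the 24-hour threshold applies to hospitalization as well as to prolongation.
3. Reconcile the readmission windows in sections 6.2.1, 2.2.2 and 4.5.

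Once the criteria govern, VTE and NICU stays need no separate conditional entries. The cost is a protocol wording change, an update to the SAE form and a few more SAE reports. No visits or procedures are added.
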